		9.3.4. Access to Information for Auditing or Inspections9.3.5. Study Discontinuation	
10.	DEEDI	RENCES	
10. 11.			
11.	APPENDICES		

Appendix 1.	Investigator Signature Page	
Appendix 2.	Study Procedures Table	
Appendix 3.	Pregnancy Precautions, Definition for Female of Childbearing Potential, and	
	Contraceptive Requirements	
Appendix 4.	Child-Pugh-Turcotte (CPT) Classification of the severity of cirrhosis	

LIST OF IN-TEXT TABLES

Table 3-1.	Biomarkers
	List of Prohibited Medications

LIST OF IN-TEXT FIGURES

Figure 3-1.	Overall Study Design	34
-------------	----------------------	----

[figure not shown]
PROTOCOL SYNOPSIS

Gilead Sciences, Inc. [name]

Study Title:	A Phase 2, Double-Blind, Randomized Study Evaluating the Safety, Tolerability, and Efficacy of GS-4997 in Combination with Prednisolone versus Prednisolone Alone in Subjects with Severe Alcoholic Hepatitis (AH)
IND Number: EudraCT Number: Clinical Trials.gov	129570 2016-000821-37
Identifier:	NCT02854631
Study Centers Planned:	Multiple centers in North America and Europe
Number of Subjects Planned:	Up to 120 subjects will be randomized in order to obtain 100 subjects with biopsy-proven severe AH
Target Population:	Males and non-pregnant, non-lactating females between 18-70 years of age with histologically-confirmed severe alcoholic hepatitis (Maddrey's Discriminant Function [Maddrey's DF] \geq 32).
Duration of Study:	Participation in the study can last up to 26 weeks, which includes a 2-week Screening period, a 4-week treatment period, and a 20-week post treatment period.
Objectives:	The primary objective of this study is as follows:
	To evaluate the safety and tolerability of GS-4997 in combination with prednisolone versus prednisolone alone in subjects with severe AH.
	The secondary objectives of this study are as follows:
	• To assess changes in hepatic synthetic function [liver biochemistry, Model for End-Stage Liver Disease [MELD] score, Child-Pugh score, the Lille model, and Maddrey's Discriminant Function (Maddrey's DF)];

- To assess mortality at 28 days, 8 weeks, 12 weeks, and 24 weeks;
- To determine the incidence of liver transplantation;
- To determine the incidence of hepatorenal syndrome (HRS);
- To determine the incidence of infection;
- To assess length of hospital stay.

The exploratory objectives of this study are:

Study Design:	This is a Phase 2, double blind, proof-of-concept, randomized study evaluating the safety, tolerability, and biological activity of GS-4997 in combination with prednisolone versus prednisolone alone in subjects with severe, histologically-confirmed AH.
	Up to 120 subjects (for 100 evaluable AH subjects) will be randomized within strata (1:1) to either:
	1. Group A (n = 50-60):
	GS-4997 18 mg once daily + prednisolone 40 mg once daily for 28 days
	OR
	2. Group B (n = 50-60):
	GS-4997 placebo once daily + prednisolone 40 mg once daily for 28 days
	Randomization will be stratified by MELD $<$ or ≥ 25 at Screening (based on local laboratory testing).
	To allow for diagnoses inconsistent with severe AH in up to 20% of subjects based on liver biopsy findings, we will target randomization of up to 120 subjects into the study.
Diagnosis and Main	Inclusion Criteria:
Diagnosis and Main Eligibility Criteria:	 Inclusion Criteria: 1) Males and non-pregnant, non-lactating females between 18-70 years of age, inclusive based on the date of the Screening visit;
-	 Males and non-pregnant, non-lactating females between 18-70 years of age, inclusive based on the date of the
-	 Males and non-pregnant, non-lactating females between 18-70 years of age, inclusive based on the date of the Screening visit; Willing and able to give informed consent prior to any study specific procedures being performed. In subjects with hepatic encephalopathy (HE) which may impair decision-making, consent will be obtained per hospital procedures (eg, by
-	 Males and non-pregnant, non-lactating females between 18-70 years of age, inclusive based on the date of the Screening visit; Willing and able to give informed consent prior to any study specific procedures being performed. In subjects with hepatic encephalopathy (HE) which may impair decision-making, consent will be obtained per hospital procedures (eg, by Legally Authorized Representative);
-	 Males and non-pregnant, non-lactating females between 18-70 years of age, inclusive based on the date of the Screening visit; Willing and able to give informed consent prior to any study specific procedures being performed. In subjects with hepatic encephalopathy (HE) which may impair decision-making, consent will be obtained per hospital procedures (eg, by Legally Authorized Representative); Clinical diagnosis of severe AH based on all of the following: a) History of excessive alcohol consumption during the past 3 months (average of > 40 g/d of alcohol for women and
-	 Males and non-pregnant, non-lactating females between 18-70 years of age, inclusive based on the date of the Screening visit; Willing and able to give informed consent prior to any study specific procedures being performed. In subjects with hepatic encephalopathy (HE) which may impair decision-making, consent will be obtained per hospital procedures (eg, by Legally Authorized Representative); Clinical diagnosis of severe AH based on all of the following: a) History of excessive alcohol consumption during the past 3 months (average of > 40 g/d of alcohol for women and > 50 g/d for men); Aspartate aminotransferase (AST) ≥ 50 U/L, based on local laboratory results; AST/alanine aminotransferase (ALT) ratio (AST/ALT) ≥ 1.5, based on local laboratory results;
-	 Males and non-pregnant, non-lactating females between 18-70 years of age, inclusive based on the date of the Screening visit; Willing and able to give informed consent prior to any study specific procedures being performed. In subjects with hepatic encephalopathy (HE) which may impair decision-making, consent will be obtained per hospital procedures (eg, by Legally Authorized Representative); Clinical diagnosis of severe AH based on all of the following: a) History of excessive alcohol consumption during the past 3 months (average of > 40 g/d of alcohol for women and > 50 g/d for men); Aspartate aminotransferase (AST) ≥ 50 U/L, based on local laboratory results; AST/alanine aminotransferase (ALT) ratio (AST/ALT)

- 4) All female subjects of childbearing potential must agree to use a highly effective method of contraception during intercourse from the Screening visit throughout the study period and for 90 days following the last dose of study drug. If females utilize hormonal agents as one of their contraceptive methods, the same hormonal methods must have been used for at least 3 months before study dosing. Females on hormonal methods must also utilize a barrier method as another form of contraception as described in Appendix 3;
- 5) Male subjects must agree to use condoms during intercourse from Screening through study completion and for 90 days following the last dose of study drug;
- Male subjects must refrain from sperm donation from Screening through at least 90 days following the last dose of study drug;
- Female subjects must refrain from egg donation or harvest for 90 days after last dose of study drug;
- 8) Willing and able to comply with scheduled visits, drug administration plan, laboratory tests, other study procedures, and study restrictions.

Exclusion Criteria:

- 1) Pregnant or lactating females;
- Other causes of liver disease including chronic hepatitis B (hepatitis B surface antigen [HBsAg] positive), chronic hepatitis C (HCV RNA positive), acetaminophen hepatotoxicity, biliary obstruction, and autoimmune liver disease;
- 3) Serum AST > 400 U/L or ALT > 300 U/L, based on local laboratory results;
- 4) MELD > 30 at Screening, based on local laboratory results;
- 5) Maddrey's DF > 60 at Screening, based on local laboratory results;
- 6) Grade 4 HE by West Haven criteria;
- 7) Concomitant or previous history of hepatocellular carcinoma;
- 8) History of liver transplantation;
- 9) HIV Ab positive;
- 10) Clinical suspicion of pneumonia;

- 11) Uncontrolled sepsis;
- 12) Uncontrolled gastrointestinal (GI) bleeding or controlled GI bleeding within 7 days of Screening that was associated with shock or required transfusion of more than 3 units of blood;
- Type 1 hepatorenal syndrome (HRS) or renal failure defined as a serum creatinine > 221 μmol/L (> 2.5 mg/dL) or the requirement for renal replacement therapy;
- 14) Subjects dependent on inotropic (eg, epinephrine or norepinephrine) or ventilatory support (ie, endotracheal intubation or positive-pressure ventilation);
- 15) Portal vein thrombosis;
- 16) Acute pancreatitis;
- 17) Cessation of alcohol consumption for more than 2 months before Baseline/Day1;
- 18) Severe associated disease (eg, cardiac failure, acute myocardial infarction, severe cardiac arrhythmias, severe pulmonary disease, neurologic disease) that may lead to premature mortality within the study period;
- 19) Malignancy within the 2 years prior to Screening, with the exception of specific cancers that have been cured by surgical resection (eg, basal cell skin cancer). Subjects under evaluation for possible malignancy are not eligible;
- 20) Positive urine screen for amphetamines, cocaine or opiates (ie, heroin, morphine) at Screening. Subjects on stable methadone or buprenorphine maintenance treatment for at least 6 months prior to Screening may be included in the study. Subjects with positive cannabis drug screen may be included in the study. Subjects with a positive urine drug screen due to prescription opioid-based medication are eligible if the prescription and diagnosis are reviewed and approved by the investigator;
- 21) Treatment with immunosuppressive drugs [budesonide, tacrolimus, sirolimus, cyclosporine, azathioprine, mycophenolate mofetil, and methotrexate], pentoxifylline, N-acetylcysteine (NAC), or granulocyte (macrophage) colony-stimulating factor within 6 months of Screening. Subjects will be eligible to enroll if systemic corticosteroids were started within 3 days prior to the Baseline/Day 1 visit. Inhaled and topical corticosteroids are allowed;

	22) Use of strong CYP3A4 inducers (eg carbamazepine, phenytoin, rifampin, St. John's wort) within 2 weeks of the Baseline/Day 1visit;
	23) Active ocular herpes simplex;
	24) Any laboratory abnormality or condition that, in the investigator's opinion, could adversely affect the safety of the subject or impair the assessment of study results;
	25) Participation in another investigational study of a drug or device within 1 month prior or within 5 half-lives of the prior investigational agent (whichever is longer) prior to Screening;
	26) Concurrent participation in another therapeutic clinical study;
	27) Known hypersensitivity to the study drugs (GS-4997 and prednisolone), the metabolites, or formulation excipients;
	28) Presence of any condition that could, in the opinion of the investigator, compromise the subject's ability to participate in the study, such as history of substance abuse other than alcohol use or a psychiatric or medical condition;
	29) Unavailable for follow-up assessment or concern for subject's compliance with the protocol procedures;
Study Procedures/ Frequency:	Screening assessments should be completed within 14 days of Baseline/Day 1 visit. Eligibility will be based on local laboratory testing. Refer to Section 6.9.10 Screening Laboratory Assessments for additional details.
	After the Screening period and a randomization visit at Baseline/Day 1, study visits will occur on Weeks 1, 2, 3, 4, 6, 8, 12, 16, 20, and 24. At minimum, vital signs, physical examination (PE), HE and ascites assessment, safety laboratory tests, alcohol consumption, and concomitant medications will be done at every visit. AEs will be collected up to 30 days after the last dose of any study drug and SAEs will be collected throughout the study.
	During the hospitalization period, subjects will be evaluated daily with assessments to include a review of adverse events, concomitant medications, study drug adherence, and a symptom-directed PE including assessments for ascites and HE. Findings based on these assessments and laboratory investigations obtained by treating physicians as part of routine care will be assessed by the investigator for triggers that may necessitate further evaluation and/or treatment discontinuation and managed per Section 7 of the protocol.

PPD

Screening assessments will include complete medical history, PE including vital signs, HE, ascites, hepatorenal syndrome (HRS) and infection assessment, laboratory assessments (hematology, chemistry, coagulation tests, HIV serology, hepatitis B and C serologies, and urinalysis), pregnancy tests (for females of child-bearing potential), liver biopsy, liver ultrasound, standard 12-lead ECG, chest x-ray, AUDIT / SADQ questionnaires, adverse events and concomitant medication assessment.

Recent gastrointestinal bleeding:

Gastrointestinal bleeding will be treated and the subject stabilized during the Screening period for at least 48 hours prior to randomization.

Sepsis:

All subjects will be screened for infection with chest radiography, urinalysis, urine culture, paracentesis with ascitic fluid (if clinically-detectable ascites is present) cell count, differential, and culture, and blood cultures (all laboratory and imaging tests performed locally). Sepsis will be defined as the presence of any positive culture or the requirement for initiation of antibiotics due to clinical or radiological signs of infection. Culture-negative pyrexia and leukocytosis on their own will not be regarded as signs of active sepsis since these findings are often seen in subjects with AH without infection. Subjects with evidence of sepsis should be treated according to the following guidelines:

Spontaneous bacterial peritonitis (SBP): AASLD Practice Guidelines: Management of Adult Patients with Ascites Due to Cirrhosis: Update 2012. (http://www.aasld.org/publications/practice-guidelines-0#practice_guidelines_accordion-block-2). Minimum recommended duration of antibiotic treatment is 5 days, and repeat ascitic fluid analysis must show a greater than 50% reduction in the number of neutrophils prior to randomization. If the initial ascitic fluid culture was positive, a repeat ascitic fluid culture should be negative prior to randomization. Patients with SBP who also have a serum creatinine >1 mg/dL, blood urea nitrogen >30 mg/dL, or total bilirubin >4 mg/dL should also receive 1.5 g albumin per kg body weight within 6 hours of detection and 1.0 g/kg 2 days later.

- Urinary tract infection (UTI): American Urological Association Adult UTI Guidelines (2016) (https://www.auanet.org/education/adult-uti.cfm). Minimum recommended duration of antibiotic treatment is 5 days for uncomplicated UTI, 7 days for uncomplicated UTI in patients with diabetes, and 14 days for complicated UTI. If the initial urine culture is positive, patients must have a repeat urine culture that is negative prior to randomization.
- Other infections: Investigator's discretion.

Once the subject has been treated for infection for a minimum of 2 days, and the sepsis is deemed under control by the investigator, the subject may continue Screening and be randomized if eligible within the Screening period If the initial blood culture is positive, patients must have a repeat blood culture that is negative prior to randomization.

Eligible subjects will be randomized to one of the two treatment groups. Prior to initial dosing, required Baseline/Day 1 assessments will be performed and will include vital signs, PE, HE, ascites, HRS and infection assessment, laboratory assessments, pregnancy tests (for females of child-bearing potential), and review of adverse events, concomitant medication, CLDQ questionnaire and alcohol consumption.

While on study, subjects will undergo the following procedures and laboratory assessments:

- CLDQ questionnaire at Baseline/Day 1, Weeks 4 and 24
- Sparse PK Sampling at Baseline/Day 1 and at Weeks 1, 2 and 4
- Blood for Biomarkers at Screening, Baseline/Day 1, and at Weeks 1, 2, 4, 8, 12 and 24
- Urine collection for Biomarkers at Baseline/Day 1, and at Weeks 4 and 24
- ELFTM Test and LOXL2 at Baseline/Day 1 and at Weeks 4, 12 and 24
- FibroScan (if available and in subjects without ascites) at Baseline/Day 1 and at Weeks 4 and 24
- 12-lead ECGs at Screening, Baseline/Day 1, and at Weeks 4 and 8

[figure not shown]
Treatment will be administered for 28 days inclusive of inpatient, and if applicable, outpatient periods.
Up to 60 subjects per arm will be randomized in order to obtain 50 subjects in each arm for the full analysis set (ie, subjects randomized with histologically-proven severe AH who took at least one dose of study drug)
 Treatment Group B: GS-4997 placebo (1 tablet) AND prednisolone 40 mg (4 x 10 mg tablets) administered orally once daily; n=50-60 subjects
• Treatment Group A: GS-4997 18 mg (1 x 18 mg tablet) AND prednisolone 40 mg (4 x 10 mg tablets) both administered orally once daily; n=50-60 subjects
PPD
Intensive PK Sub-study
• Stool collection at Baseline/Day 1 and at Weeks 4 and 24.
 Urine collection at Screening (for drug screen, pregnancy screen, and to rule out infection)
• Hemoglobin A1c at Baseline/Day 1 and at Weeks 12, and 24
 Blood glucose, insulin and lipid profile at Screening, Baseline/Day 1 and at Weeks 4, 12 and 24

Criteria for Evaluation:

Cafatan	Cafate will be avaluated by avamining the insidence of treatment
Safety:	Safety will be evaluated by examining the incidence of treatment emergent adverse events, including serious adverse events, clinical laboratory tests, ECGs, and vital signs.
	An independent, external Data Monitoring Committee (DMC) that includes two hepatologists and a PhD statistician will convene prior to study start, once 20 subjects have been treated for 28 days, and every 3 months thereafter to monitor the study for safety events including SAEs, deaths, premature discontinuation of treatment for AEs, grade 3 and higher AEs, grade 3 and higher treatment-emergent laboratory abnormalities, and individual stopping criteria for GS-4997/placebo study drug (see Section 7.5). The DMC will also evaluate (based on an unblinded review of safety data) and monitor for trial stopping criteria (see Section 8.11).
Efficacy:	The biological activity of prednisolone and the combination of GS-4997 and prednisolone will be evaluated using clinical outcomes and biomarker variables.
Pharmacokinetics:	The plasma concentration of GS-4997 and its metabolite, GS-607509, will be determined. The plasma concentration of other GS-4997 metabolites and/or prednisolone may be explored. PK samples may also be used to measure protein-binding of GS-4997 and/or its metabolites. PPD
Statistical Methods:	
	Primary Endpoint:
	The primary endpoint is the safety of GS-4997 in combination with prednisolone versus prednisolone alone in subjects with severe AH. The primary analysis will be conducted when all subjects have been followed for 30 days after their last dose of study drug or been prematurely terminated from study.
	Secondary Endpoints:
	Clinical outcomes
	— Mortality at 28 days, 8 weeks, 12 weeks, and 24 weeks
	— HRS
	— Infection
	— Length of hospital stay

- Liver transplantation
- Measures of hepatic synthetic function:
 - Change from baseline in liver biochemistry: ALT, AST, GGT, albumin, alkaline phosphatase, bilirubin, and INR
 - Lille response (score < 0.45) at Day 7, Lille null response (score ≥ 0.56) at Day 7, Lille score at Day 7 as a continuous variable, and combined score including Lille score at Day 7 and baseline MELD score
 - Change from baseline in prognostic indices: MELD, Child-Pugh score, Maddrey's DF

Exploratory Endpoints:

Efficacy Analysis:

The biological activity of prednisolone and the combination of GS-4997 and prednisolone will be evaluated using clinical outcomes and measures of hepatic synthetic function. PPD

Exploratory Analysis:

Safety Analysis:

All safety data collected will be listed and summarized, as appropriate, by treatment group. Safety endpoints will be analyzed by the number and percent of subjects with events or abnormalities for categorical variables or 8-number summary (n, mean, standard deviation, median, Q1, Q3, minimum, maximum) for continuous variables by treatment group.

Pharmacokinetic Analysis:

GS-4997 and GS-607509 plasma concentrations will be listed and summarized for all subjects. PPD

Sample Size:

The number of subjects was chosen based on clinical experience with other similar proof-of-concept studies. PPD

This study will be conducted in accordance with the guidelines of Good Clinical Practice (GCP) including archiving of essential documents.

GLOSSARY OF ABBREVIATIONS AND DEFINITION OF TERMS

° C	degrees Celsius
° F	degrees Fahrenheit
ADR	adverse drug reaction
AE	adverse event
AH	Alcoholic Hepatitis
ALT	alanine aminotransferase
ARA	acid reducing agent
ASK1	apoptosis signal-regulating kinase 1
ASK1 ^{-/-}	apoptosis signal-regulating kinase 1 deficient
AST	aspartate aminotransferase
ATP	Adenosine triphosphate
AUC _{tau}	area under the plasma concentration versus time curve over the dosing interval (tau)
AUDIT	Alcohol Use Disorders Identification Test
β-hCG	beta human chorionic gonadotropin
BAP	Biomarker Analysis Plan
BMI	body mass index
BUN	blood urea nitrogen
CBC	complete blood count
сс	cubic centimeter
CI	confidence interval
CK18	cytokeratin (C18)
CL _{cr}	creatinine clearance
C _{last}	last observed quantifiable plasma/serum concentration of the drug
C _{max}	maximum observed plasma/serum concentration of drug
CLDQ	Chronic Liver Disease Questionnaire
CRO	contract (or clinical) research organization
CSR	clinical study report
CTCAE	Common Terminology Criteria for Adverse Events
CYP3A4	cytochrome P4503A
DKD	Diabetic kidney disease
dL	Deciliter
DMC	Data Monitoring Committee
DSPH	Drug Safety and Public Health
DF	(Maddrey's) Discriminant Function
DP	drug product
EC	ethics committee
ECG	electrocardiogram

eCRF	electronic case report form
EDC	electronic data capture
eg	example
ELF [™] Test	enhanced liver fibrosis test
ЕоТ	End of Treatment
EU	European Union
FAS	Full analysis set
FDA	(United States) Food and Drug Administration
FIO ₂	Fraction of Inspired Oxygen
FSH	Follicle-stimulating hormone
GGT	gamma glutamyl transferase
GI	gastrointestinal
GMP	Good Manufacturing Practice
GSI	Gilead Sciences, Inc.
HbA1c	Hemoglobin A1c
HBsAg	Hepatitis B surface antigen
HBV	Hepatitis B virus
HCC	Hepatocellular Carcinoma
hCG	human chorionic gonadotropin
Hct	Hematocrit
HCV	Hepatitis c virus
HDL	High-density lipoprotein
HDPE	High-density polyethylene
HE	hepatic encephalopathy
Hg	Hemoglobin
HIV	Human immunodeficiency virus
HLT	high-level term
HLGT	high-level group term
HOMA-IR	homeostatic assessment of insulin resistance
HRS	Hepatorenal Syndrome
IB	Investigator's Brochure
ICF	Informed Consent Form
ICH	International Conference on Harmonisation of Technical Requirements for Registration of Pharmaceuticals for Human Use
ID	Identification
IEC	independent ethics committee
IEC	institutional ethics committee
IMP	Investigational Medicinal Product
IND	Investigational New Drug (Application)
INR	international normalized ratio

IRB	institutional review board
IUD	intrauterine device
IVD	In vitro diagnostic
IWRS	interactive web response system
kg	Kilogram
LOX	Lysyl oxidase
LOXL1	Lysyl oxidase-like 1
LOXL2	Lysyl oxidase-like 2
LOXL3	Lysyl oxidase-like 3
LOXL4	Lysyl oxidase-like 4
LPS	lipopolysaccharide
mAB	monoclonal antibody
MedDRA	Medical Dictionary for Regulatory Activities
MELD	Model for End-Stage Liver Disease
μg	Microgram
mg	Milligram
min	Minute
mL	Milliliter
mm	Millimeter
mm Hg	millimeters of mercury
NAC	N-acetylcysteine
NASH	Nonalcoholic steatohepatitis
РАН	Pulmonary arterial hypertension
PE	Physical Exam
РК	Pharmacokinetic
pН	measure of the acidity
РТ	preferred term
РТ	prothrombin time
PTM	Placebo to match
PTT	Partial prothrombin time
q	Every
QoL	Quality of Life
QT	electrocardiographic interval between the beginning of the Q wave and termination of the T wave, representing the time for both ventricular depolarization and repolarization to occur
RNA	ribonucleic acid
ROW	rest of world
SADQ	Severity of Alcohol Dependence Questionnaire
SADR	serious adverse drug reaction
SAE	serious adverse event

SAP	statistical analysis plan
SBP	Spontaneous bacterial peritonitis
SC	Subcutaneous
SOP	standard operating procedure
SUSAR	Suspected Unexpected Serious Adverse Reaction
$\mathbf{t}_{\mathbf{y}_2}$	An estimate of the terminal elimination half-life of the drug in serum/plasma/PBMC, calculated by dividing the natural log of 2 by the terminal elimination rate constant (λ_z)
TEAEs	Treatment emergent adverse events
T _{last}	last measured concentration
T _{max}	time (observed time point) of C _{max}
TQT	thorough QT
ULN	upper limit of the normal range
US	United States
UTI	Urinary tract infection
wks	weeks

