1.5. Risk/Benefit Assessment for the Study

The primary risk of study participation relates to the proposed initiation of prednisolone \pm GS-4997 prior to the histologic confirmation of AH. The rationale for this approach is two-fold. First, in many centers, performance of liver biopsy in subjects with suspected severe AH is not standard of care prior to initiating treatment, typically with prednisolone. Second, the planned approach will allow the rapid initiation of therapy which is deemed vital to optimize outcomes in subjects with severe AH. Importantly, a clinical diagnosis of AH (as per standard of care) will be made and contraindications to prednisolone (e.g. untreated infection) will be excluded in all subjects prior to starting treatment.

Another related risk of study participation is that some subjects who do not have alcoholic hepatitis will be exposed to prednisolone \pm GS-4997 therapy for up to 7 days before the diagnosis is refuted on biopsy. Based on prior studies, an estimated 20% of subjects who are suspected of severe alcoholic hepatitis do not have confirmation of the diagnosis on biopsy. As mentioned above, the initiation of prednisolone in subjects with suspected alcoholic hepatitis without performance of a liver biopsy is standard practice in many centers. The plan to discontinue treatment in subjects in whom the biopsy does not confirm alcoholic hepatitis is a potential benefit of study participation because it will limit exposure to prednisolone, which has toxicities including infection and worsened glycemic control The risk of short-term exposure to GS-4997 is low based on the results of prior Phase 1 and 2 studies (as outlined in Section 1.2.3), including the hepatic impairment study (GS-US-223-1018) that included subjects with mild, moderate, and severe hepatic dysfunction.

In view of the potential for GS-4997 to reduce major mechanisms of liver injury in subjects with severe alcoholic hepatitis, the limitations in available therapy, existing safety data, and the proposed study design to carefully monitor patient safety, the benefit/risk balance for this study is considered positive.

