3.2. Treatment Plan and Regimen

This is a Phase 2 double blind, randomized study evaluating the safety, tolerability, and biological activity of GS-4997 in combination with prednisolone versus prednisolone alone in subjects with severe, histologically-confirmed AH.

Up to 120 subjects will be randomized in a 1:1 ratio (within strata) to 1 of 2 treatment groups:

- Group A (n = 50-60): GS-4997 18 mg once daily + prednisolone 40 mg once daily for 28 days
- Group B (n = 50-60): GS-4997 placebo once daily + prednisolone 40 mg once daily once daily for 28 days

Randomization will be stratified by MELD < 25 or \ge 25 at Screening as calculated using local laboratory tests and an online MELD calculator (see Section 6.9.7).

The full analysis set will comprise 100 subjects but up to 120 subjects will be randomized to account for subjects in whom AH is not confirmed on liver biopsy. The full analysis set includes those randomized and dosed with histologically-proven severe AH. Safety data will be reported for all subjects who take study drug.

All subjects with liver biopsies consistent with severe AH and negative HBV, HCV, and HIV serologies who complete study drug should complete Screening, on-treatment, and post-treatment assessments as outlined in Appendix 2. Subjects discontinuing both study drugs prior to Week 2 should complete an end of treatment visit after stopping drug, a 30-day safety FU visit, and all post-treatment follow-up visits. Subjects discontinued after Week 2 should complete an end of treatment assessments as outlined in Appendix 2.

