4. SUBJECT POPULATION

4.1. Number of Subjects and Subject Selection

The full analysis set will comprise 100 subjects, males and non-pregnant, non-lactating females between 18-70 years of age with histologically-confirmed severe AH (Maddrey's DF \geq 32). Up to 20 additional subjects will be randomized to account for subjects in whom AH is not histologically-confirmed.

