# 1.2. Study Design

This is a Phase 2, randomized, double-blind, proof-of-concept study evaluating the safety, tolerability, and biological activity of selonsertib in combination with prednisolone versus prednisolone alone in subjects with severe, histologically-confirmed AH. Subjects are 18 to 70 years of age, with a history of excessive alcohol consumption (average of > 40 g/day of alcohol for women and > 50 g/day of alcohol for men); AST  $\geq$  50 and  $\leq$  400 U/L; ALT  $\leq$  300 U/L; AST/ALT ratio  $\geq$  1.5; onset of jaundice within the past 3 months; a screening Maddrey DF score  $\geq$  32 and  $\leq$  60; and a MELD score  $\leq$  30. Subjects consented under Amendment 1 of the study protocol will qualify for the study and be stratified based on the screening MELD score calculated using central laboratory results while all other subjects will qualify for the study and be stratified based on the screening MELD score calculated using local laboratory results. All analyses of laboratory values for efficacy and safety will be based on central laboratory (ie, Covance Laboratories, Inc.) results except for the specific cases for Lille and MELD scores described in Section 3.6.1.

Up to 120 subjects will be randomized to obtain 100 subjects with histologically-proven severe AH who are evaluable for the Full Analysis Set (FAS). Subjects meeting the study's entry criteria will be randomly assigned within strata (screening MELD < 25 or  $\geq$  25) to one of the following 2 treatment groups in a 1:1 ratio:

- Group A (n = 50-60): Selonsertib 18 mg QD + Prednisolone 40 mg QD for 28 days
- Group B (n = 50-60): Selonsertib Placebo QD + Prednisolone 40 mg QD for 28 days

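### At the plan's own 20% biopsy non-confirmation rate, 120 randomised subjects give about 96 in the Full Analysis Set, not 100

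*Protocol*

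**What the plan says.** The Protocol Synopsis (Study Design) sets the numbers and gives the reason for them. It states "Up to 120 subjects (for 100 evaluable AH subjects) will be randomized within strata (1:1) to either" of two groups, and explains the excess over 100 as follows: "To allow for diagnoses inconsistent with severe AH in up to 20% of subjects based on liver biopsy findings, we will target randomization". The cap is 120. The treatment part of the synopsis gives the per-arm version: "Up to 60 subjects per arm will be randomized in order to obtain 50 subjects in each arm for the full analysis set". The footnote to Figure 3-1 repeats it.

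Section 1.5 gives the source of the rate. From prior studies, "an estimated 20% of subjects who are suspected of severe alcoholic hepatitis do not have confirmation of the diagnosis on biopsy".

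Section 3.2 states the outcome as a fact: "The full analysis set will comprise 100 subjects but up to 120 subjects will be randomized". Section 4.1 describes the allowance as a count added to 100: "Up to 20 additional subjects will be randomized to account for subjects in whom AH is not histologically-confirmed".

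SAP Section 1.2 carries the totals forward: "Up to 120 subjects will be randomized to obtain 100 subjects with histologically-proven severe AH". It gives 50 to 60 per group, but restates neither the 20% nor a figure of 50 per arm in the FAS.

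Membership of the FAS (Protocol Section 8.3.1.1, SAP Section 3.1.3) requires at least one dose of study drug and histologically confirmed severe alcoholic hepatitis (AH). Both documents make it the primary set for efficacy.

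**The concern.** The synopsis and Section 1.5 express the loss as a percentage of subjects entering with a clinical diagnosis. Section 4.1 turns it into 20 extra subjects on top of 100, which is 20% of the evaluable target and not 20% of those randomised. The two differ, and 120 is a cap, so the plan has no room to make up the difference.

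At stake is the stated size of the primary efficacy set. A reader would plan on 50 per arm, and any precision or power figure based on 50 would be slightly optimistic.

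**Working it through.** **Inputs**

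- Non-confirmation rate d = 0.20 (Synopsis, Study Design, as a ceiling; Section 1.5, as an estimate).
- Evaluable target 100, or 50 per arm (Synopsis; Sections 3.1 to 4.1; the total also in SAP 1.2).
- Maximum randomised 120, or 60 per arm (same places).
- 1:1 allocation within strata (Section 3.2).

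**Reproducing the plan's figure**

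100 × (1 + 0.20) = 120, and 50 × 1.20 = 60. These match the plan, so the 20% was applied to the evaluable number.

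**Inflation with the rate applied to those randomised**

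N = n / (1 − d) = 100 / 0.80 = 125. Per arm, 50 / 0.80 = 62.5, so 63, or 126 in total.

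**Yield of the planned 120**

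- Lost: 120 × 0.20 = 24, against the 20 allowed for.
- Remaining: 120 × 0.80 = 96 in total; 60 × 0.80 = 48 per arm.
- Rate that 20 extra subjects can absorb: 20 / 120 = 16.7%.

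**Chance of reaching the target**

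This treats confirmations as independent, with all 120 subjects dosed and 60 in each arm.

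- Total: P(X ≥ 100) for X ~ Binomial(120, 0.80) = 0.21.
- One arm: P(X ≥ 50) for X ~ Binomial(60, 0.80) = 0.323. Both arms: 0.323² = 0.10.

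**Sensitivity to the rate, with 120 randomised**

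| Non-confirmation | Expected FAS | P(FAS ≥ 100) |
|---|---|---|
| 10% | 108 | 0.99 |
| 15% | 102 | 0.74 |
| 16.7% | 100 | 0.56 |
| 20% | 96 | 0.21 |

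**Effect on precision**

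Interval width scales as 1/√n, so moving from 50 to 48 per arm widens intervals by √(50/48) = 1.02, about 2%.

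**Losses not quantified**

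Subjects randomised but never dosed also leave the FAS. Inadequate biopsies with no alternative diagnosis allow the subject to stay in the study (Sections 3.2 and 6.9.1), but do not supply the histological confirmation that the FAS requires. The documents give no rate for either, so neither is in the figures above.

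**The case against.** The best counter-argument concerns the denominator. Section 1.5 speaks of suspected cases, and biopsy is nominally a screening procedure. A suspected subject whose negative result is known before randomisation would not be randomised. If a share f of suspected subjects has a result by then, non-confirmation among those randomised is 0.2(1 − f) / (1 − 0.2f). At f = 0.20 this is 0.16 / 0.96 = 16.7%, exactly the rate at which 120 gives 100.

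The algebra is right, but f appears nowhere in the documents and the plan does not invoke it. The synopsis offers the 20% as the direct reason for randomising more subjects, which makes sense only as a loss after randomisation. Section 1.5 uses the same rate when discussing subjects already exposed to study drug before biopsy refutes the diagnosis.

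A second argument is that 20% is a ceiling, so 96 is a worst case. It is true that lower rates give 100 or more. But an allowance for losses of up to 20% has to work at 20%, and Section 1.5 uses 20% as the estimate itself.

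Several smaller points stand:

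- The SAP repeats 120 for 100 without the 20%, so it contains no contradiction on its own.
- Section 1.5's wording could already include inadequate samples, so these may not be a wholly separate loss.
- The visible sample-size text (Protocol 8.10, SAP 1.3) cites only clinical experience and what follows is redacted, so no power statement can be shown to be wrong.
- The primary endpoint is safety in all dosed subjects, and a modified intent-to-treat efficacy analysis that does not depend on biopsy is also planned.

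These limit the importance of the point but do not make the arithmetic agree.

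**Conclusion.** The concern holds. At the plan's own 20% rate the expected FAS is 96 (48 per arm), 4% below the stated 100 (50 per arm), with about a 21% chance of reaching 100. This rests on applying the 20% to randomised subjects, as the synopsis does, and on every randomised subject being dosed; undosed subjects would lower the figure. The practical effect is minor, but the size of the primary efficacy set is stated as a fact that the plan's own assumption does not deliver, so it should be corrected.

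**What to change.** Restate the size in the Protocol Synopsis, Sections 3.1, 3.2 and 4.1, and SAP Section 1.2: up to 120 randomised is expected to give about 96 FAS subjects (48 per arm) at 20% non-confirmation, and 100 only if the rate is 16.7% or lower. Say explicitly that the rate refers to randomised subjects. Recalculate on 48 per arm any precision or power statement that uses 50, including any in the redacted text.

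The cost is wording only. Enrolment, treatment and the analyses are unchanged; the stated evaluable number becomes slightly less favourable.
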